10.1.8 Action taken for protocol treatment

As for action concerning protocol treatment, when protocol treatment is discontinued as an action against the concerned adverse event, it will be defined as “discontinuation”.

10.1.9 Outcome

Outcome of adverse events is classified as follows.

Category	Criteria for judgment
Recovered	
• disappearance or recovery of symptoms and findings• laboratory values returned to normal or baseline
Improved	
• severity was improved by one or more grades• symptoms or findings mostly disappeared• laboratory values improved but has not returned to normal or baseline• when the subject died from a cause other than the adverse event concerned while the event was resolving
Not recovered	
• no change in symptoms, findings, or laboratory data• the symptoms, findings, or laboratory data on the final day of observable period aggravated compared with the date of onset• irreversible congenital anomaly• when a subject died where the concerned adverse event is not a direct cause of death and the concerned adverse event remained not recovered
Recovered with sequelae	
• disability which disturbs daily life
Death	
• direct relationship between death and the concerned adverse event• “Direct relationship” means that the concerned adverse event was the cause of death, or the concerned adverse event was clearly responsible for death.• Outcome of an adverse event which was not determined (judged, presumed) a direct cause of death observed in the same subject is not considered as death.
Unknown	
• follow-up specified in the protocol after the date of onset was not possible due to change of hospitals or relocation, etc.

10.2 Procedures

10.2.1 Collection and reporting of adverse events

10.2.1.1 Period for collection of adverse events

Adverse events should be continuously collected from initiation of protocol treatment up to 4 weeks (28 days) after discontinuation of protocol treatment or initiation of follow-up treatment, whichever date is earlier. In addition, adverse event causal relationship cannot be ruled out of protocol treatment collected later 4 weeks (28 days) after discontinuation of protocol treatment or initiation of follow-up treatment.

CONFIDENTIAL

10.2.1.2 Reporting of adverse events

At each visit of subject, the investigator or the subinvestigator should confirm whether the onset of subjective symptoms is present or not. Onset of any adverse event that developed after the previous visit should be checked by asking a question such as “how has your condition been since the last visit?” to a subject.

The investigator or the subinvestigator should follow up all subjects who developed adverse events irrespective of a causal relationship with protocol treatment until disappearance of symptoms or abnormal laboratory values, return of clinically problematic abnormal laboratory values to the value before administration of study drug, or if not, until observed changes can be sufficiently explained for other events (persistent/irreversible adverse event, etc.).

All adverse events should be entered into the CRF. The name of the adverse event, date of onset, severity, seriousness, causal relationship with protocol treatment (unrelated or related), further if event has causal relationship “related” to protocol treatment, causal relationship with panitumumab (unrelated or related) should be recorded. Also, for the last course, action taken and outcome concerning protocol treatment as well as date of resolution should be recorded.

Follow-up period of adverse events is until recovery of an adverse event, or the investigator or the subinvestigator judges that further follow-up would be unnecessary.

10.2.2 Collection and reporting of serious adverse events

When a serious adverse event develops during the period of collecting adverse events, it should be reported according to the following procedures.

When the investigator or the subinvestigator judges that a serious adverse event has occurred based on the reporting by a subject, etc., or results of various tests, imaging findings or definitive diagnosis, etc., it should be reported immediately to the director of the study site.

Also, the investigator or the subinvestigator should report to the sponsor (see attached sheet for contact information) within 72 hours of recognition of onset of event. Further, the investigator should submit a formal report within 10 calendar days to the sponsor.

Furthermore, the content below which is to be reported to the sponsor within 72 hours is mandatory, and other items should be reported as much as possible.

- Brief description of adverse event and the reason for why it was determined as serious
- Study title

- Subject ID code
- Name of study site
- Name of investigator or the subinvestigator
- Name of protocol treatment being conducted
- Determined causal relationship

10.2.3 Follow-up of serious adverse events

The investigator or the subinvestigator should follow-up all serious adverse events, etc., until recovery is confirmed, or the final outcome is determined.

When a change such as alteration of outcome was made to the report of a serious adverse event, the investigator or the subinvestigator should submit a report specifying details of the change to the director of study site and the sponsor. When requested by the sponsor or the study site committee such as the ethics review committee, related data of the study site (e.g., ECG, laboratory test values, summary of discharge report, result of autopsy, etc.) should be provided.

10.2.4 Reporting of additional information concerning adverse events

If the sponsor requests provision of additional information concerning adverse events for reporting to regulatory authorities, the investigator or the subinvestigator should confirm the necessary additional information and enter in the EDC system or submit a report within the period specified by the sponsor.

10.2.5 Dissemination of unknown serious adverse event to joint research institutions

If the director of the study site receives a report of an unexpected serious adverse event, for which a direct causal relationship with protocol treatment cannot be denied, from the investigator or subinvestigator, the director should ask the opinion of a study site committee such as the ethics review committee and add the items below to the report submitted by the investigator, and disseminate it to the monitoring committee and research institutions that are jointly conducting clinical study through the sponsor.

- Date of review, summary of review, result, necessary action, etc., related to the study site committee such as ethics review committee.

10.2.6 Reporting of serious adverse events, etc., to ethics review committee, etc., and regulatory authorities

If the director of the study site receives report of serious adverse event from the investigator, the director should ask opinion of the ethics review committee, etc., and disseminate the study sites that are conducting clinical study through the sponsor or the CRO (research secretariat office) consigned by the sponsor.

If the director of the study site receives report of unexpected serious adverse event, the director should add the items below to the report submitted by the investigator, and prepare unexpected serious adverse event report and report to the Minister of Health, Labour and Welfare, and disseminate the study sites that are conducting clinical study (report to the Minister of Health, Labour and Welfare, and dissemination to study sites through sponsor is also possible).

- Action taken for serious adverse event
(discontinuation of new enrollment, revision of ICF, re-consent from other subjects, etc.)
- Date of review, summary of review, result, necessary action, etc., related to ethics review committee, etc.
- Dissemination to joint research institutions.

The sponsor should report according to regulations, unexpected serious adverse drug reactions and other serious adverse events that are subject to emergency reporting to regulatory authorities, the investigator and director of study site.

From the time point of first acknowledging the event or receiving additional information, the sponsor or the CRO (research secretariat office) consigned by the sponsor should comply with regulatory required time frame for reporting, and make emergency report concerning unexpected serious adverse drug reactions and expected serious adverse drug reactions to regulatory authorities. Also, the sponsor should in the same way make an emergency report of other critical safety information that may have a major effect on the study drug risk-benefit, continuation of study drug administration, and continuation of clinical study. The study site should submit copies of emergency report documents to the ethics review committee, etc.

11.0 COMMITTEES ESTABLISHED FOR THIS STUDY

11.1 Research steering committee

The research steering committee will be established to effectively promote this study.

The research steering committee will consist of the sponsor, research steering committee chairman, research steering committee members and statistics representative, and the sponsor or its designee will act as the secretariat.

Details of management of the research steering committee will be specified in a separately prepared procedure manual. Research steering committee members are listed in Section 1.2.

11.2 Data monitoring committee

The Data Monitoring Committee (hereinafter referred to as DMC) will be established according to the ICH E6 (1.25), and the sponsor or its designee will serve as the secretariat of the DMC.

The purpose of the DMC is to evaluate safety report data (including DLT occurring during the DLT evaluation period of the phase I part of the study) independent of the research steering committee concerning the appropriateness of continuing the study, or changing, discontinuing, suspending, or other measures regarding the study, and to submit the results to the sponsor. The sponsor will determine whether to continue, discontinue, or change the study based on the results.

The sponsor will prepare the DMC procedures (DMC charter) specifying the details such as the objective, roles, and responsibilities of the DMC, and management procedure. DMC members are listed in Section 1.2.

CONFIDENTIAL

12.0 DATA MANAGEMENT AND STORAGE OF RECORDS

Detailed procedure of data management is described in data management plan. Adverse events and concurrent conditions should be coded using MedDRA.

12.1 Case report form

The investigator or the subinvestigator should prepare the case report form (CRF) for all subjects who have given consent.

The sponsor or its designee should provide study sites with access authorization to the electronic data capture (hereinafter referred to as EDC). The sponsor should provide the investigator, subinvestigators, and study collaborators with training for utilization of EDC. The CRF will be used to report the information collected during the study period to the sponsor. The CRF will be prepared in Japanese. Data will be directly entered in preparing the CRF.

A change or correction of the CRF will be recorded as an audit trail that records the information before and after the change or correction, the person who made the change or correction, date of change or correction, and its reason.

The investigator or its designee should ensure the accuracy and completeness of the CRF, and provide an electronic signature on the relevant page of the case report form. The investigator bear full responsibility for the accuracy and reliability of all the data entered into the CRF.

The data below will be directly recorded into the CRF.

- Seriousness, severity and causal relationship of adverse event with protocol treatment and “panitumumab”

When the investigator or the subinvestigator makes a change or correction in the data entered into the CRF after fixation of clinical data base, a record (Data Clarification Form) of change or correction in the CRF provided by the sponsor should be used. The investigator should confirm that the record of change or correction in the CRF is accurate and complete, and sign or write name/ affix a seal, and date it.

The sponsor or its designee should confirm CRF has been prepared appropriately. The sponsor or its designee should have access to the medical records of study subjects and in-house records to ensure the accuracy of the CRF as necessary. The completed CRF is the property of the sponsor, and the investigator or the subinvestigator should not disclose the information to a third party without a written permission from the sponsor.

12.2 Time limit for data input into the EDC

The sponsor or its designee should request the investigator or the subinvestigator to promptly enter EDC during the period from enrollment of subject to the end of follow-up.

It is recommended that after consent has been obtained from subject, the EDC should be entered within the time frame described below, in principle. A failure to enter the data within the time frame does not constitute a deviation, but it is recommended that it should be entered as much as possible.

1. At enrollment: within 2 weeks (14 days) after enrollment (within 1 week (7 days) of course 1 of the phase I part of the study (the DLT evaluation period))
2. During protocol treatment: within 2 weeks (14 days) after the final day of each course (the starting day of the next course) (within 1 week (7 days) of course 1 of the phase I part of the study (the DLT evaluation period))
3. At discontinuation of protocol treatment: within 4 weeks (28 days) after the day of discontinuing protocol treatment (within 2 weeks (14 days) of course 1 of the phase I part of the study (the DLT evaluation period))
4. Imaging test results: within two weeks (14 days) after evaluation of efficacy
5. Follow-up period: within two weeks (14 days) after request for follow-up
6. Inquiry about data input items: within two weeks (14 days) from inquiry

12.3 Storage of records

The investigator or the director of study site should store the following materials including those specified in Section 14.1 and study specific documents to be used by the sponsor or its designee for investigation and audit. The materials include a list of subject screening, medical records, signed and dated original consent form, and a record of change and correction of the CRF (copy)/electronic copy of electronic CRF containing audit trail. Also, the investigator and the director of study site should store the essential documents until the date that passes five years after discontinuation or completion of the study. However, when the sponsor requires a longer storage period, the director of the study site will discuss the period and methods of storage with the sponsor.

Further, the investigator and the director of the study site will store the essential documents until the sponsor notifies that storage is no longer necessary.

13.0 STATISTICAL ANALYSIS METHODS

The statistics representative or his/her designee (a personnel belonging to an institution independent from sponsor, analysis personnel) will conduct analysis. Sponsor will not be involved in analysis.

13.1 Statistical and analytical plans

The statistics representative or analysis personnel should start preparing the statistical analysis plan (SAP) (first version) and establish the SAP (first version) before conducting the final analysis. The SAP (first version) should be finalized before data fixation. Detailed definition of endpoints and analysis methods should be specified in the SAP to deal with all the purposes of the study.

Data review should be performed before data fixation. Data review is performed to evaluate the accuracy and completeness of the study data, subject evaluability, and appropriateness of the planned analysis methods.

13.2 Statistical analysis of the phase I part of the study

13.2.1 Analysis set

Two analysis sets will be created for the phase I part of the study: “set of enrolled subjects who received at least one dose of protocol treatment and satisfied all of the enrollment criteria” and the “DLT evaluation set.” The “DLT evaluation set” will be based on the definition subjects included in the DLT evaluation in Section 8.9.2.

13.2.2 Analysis of demographic and other baseline characteristics

The following analyses will be performed in “set of enrolled subjects who received at least one dose of protocol treatment and satisfied all of the enrollment criteria” and the “DLT evaluation set.”

Demographic factors will be tabulated for each subject. Frequency will be tabulated for discrete data, and summary statistics will be calculated for continuous data.

13.2.3 Safety analysis

13.2.3.1 Primary endpoint and analysis method

[Primary endpoint]

Incidence of DLT with panitumumab + TAS-102 combination therapy

CONFIDENTIAL

[Analysis method]

The incidence of DLT will be evaluated in the DLT evaluation set according to Section 6.1 Study Design (Figure 6.a Outline of study design). In addition, a table listing each DLT event that occurs will be prepared.

13.3 Statistical analysis of the phase II part of the study

13.3.1 Analysis sets

In the phase II part of the study, statistical analysis will be performed in a "full analysis set" and "safety analysis set". The "full analysis set" is the main efficacy analysis set, and is defined as "subjects enrolled in phase I and 2 who received at least one dose of protocol treatment (RD) and satisfied all of the enrollment criteria". RD is recommended dose which is confirmed in the Phase I part. The "safety analysis set" is defined as "subjects enrolled in phase I and II who received at least one dose of panitumumab and/or TAS-102". Additionally, all subjects who are enrolled in this study is defined as "all enrolled subjects".

The statistics representative and analysis personnel should finalize statistic analysis plan before data fixation based on the confirmation of the definition of analysis sets and appropriateness of analytical handling rules of the subject data in the analysis sets and addition of handling rule for the issues which are not determined at planning.

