6.0 CLINICAL STUDY DESIGN

6.1 Clinical study design

This phase I/II study is a multi-center, open-label single-arm study that consists of a phase I part (dose de-escalation) which will assess the tolerability and RD of Panitumumab in combination with TAS-102 as primary objective, and a phase II part which will assess the efficacy and safety of Panitumumab in combination with TAS-102 as primary objective in patients with RAS wild-type unresectable, advanced/recurrent colorectal cancer. In the phase I part, the subjects will be included sequentially into Cohort 1 and 2, 3 subjects each with the same dosage and administration. In the phase II part, 46 subjects will be included additionally for RD confirmed in the phase I part.

[figure not shown]

Figure 6.a Outline of study design

In the phase I part, each cohort will be conducted with 3 subjects, the sponsor will assess tolerability of the dosage and administration based on the incidence of Dose Limiting Toxicity (hereinafter referred to as DLT) during the assessment period and determine whether or not to move on to the next cohort (opinion from the Data Monitoring Committee [hereinafter referred to as DMC] will be confirmed appropriately upon determination). Therefore, in Cohort 1, if occurrence of DLT is ≤ 2 subjects out of 3, the dosage and administration will be determined tolerable and will move on to Cohort 2. However, if DLT is observed in 2 subjects during DLT assessment period in Cohort 1, subjects will be included one at a time in Cohort 2 in consideration for safety to assess DLT.

CONFIDENTIAL

Similarly 3 subjects will be included in Cohort 2 and DLT will be assessed in a total of 6 subjects of Cohort 1 and 2 at most. If DLT is observed in 3 subjects included in Cohort 1, or DLT is observed in 3 subjects from a total of 6 subjects of Cohort 1 and 2, the sponsor will promptly request to postpone new enrollment of subjects to each site and after consultation with the Research Steering Committee and DMC on the continuation of the study, will determine whether or not to continue the study.

If study is to be continued, taking in account of the adverse event that occurred, either panitumumab or TAS-102 or both drugs will be reduced one step and re-conducting the phase I part similarly will be considered. If DLT is observed in 3 subjects after reducing 1 step of panitumumab or TAS-102 or both drugs, the study will be discontinued.

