16. Patients who have adverse event from previous treatment that has not recovered to at least Grade 1 (Grade 2 for peripheral sensory neuropathy) by Common Terminology Criteria for Adverse Events (hereinafter referred to as CTCAE, Japanese edition JCOG version v4.03) (excluding hemoglobin content)
17. Patients with known BRAF mutation.
18. Other patients judged by the investigator or subinvestigator to be ineligible for enrollment in the study (such as patients who may be coerced to give consent)

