8.7 Criteria for discontinuation of protocol treatment for each subject

The number of doses is not specified. However, protocol treatment should be discontinued when any of the criteria for discontinuation of protocol treatment listed below is met. The date of discontinuation of protocol treatment is defined as the date when the investigator or the subinvestigator decides on discontinuation of protocol treatment. The investigator or the subinvestigator should record the main reason for discontinuation of protocol treatment in the case report form (hereinafter referred to as CRF) according to the classification described below. For subjects discontinuing before enrollment, see 9.3 Records of subjects who discontinued before enrollment.

1. Lack of efficacy (exacerbation)

When PD is evident in the clinical or imaging evaluation

2. Adverse event

Discontinuation of treatment due to an adverse event in the opinion of the investigator or the subinvestigator, or according to the protocol treatment discontinuation criteria. However, death during protocol treatment will be classified in “4. Death during protocol treatment” and not in this item.

Protocol treatment is postponed due to adverse event for 58 days or more after the day of starting the last course. However, postponement due to holidays is allowed.

3. Voluntary discontinuation

A subject wishes to discontinue study participation. The reason for discontinuation should be recorded in CRF when it is clarified.

CONFIDENTIAL

Note: Attempts should be made as best as possible to clarify the reason for voluntary discontinuation. (Discontinuation due to adverse event or lack of efficacy should not be classified as “voluntary discontinuation”).

4. Death during protocol treatment

Death before discontinuation of protocol treatment is decided. Date of death, reason of death (protocol treatment related, primary disease, others) should be described in the CRF.

5. Significant deviation from the protocol

When study continuation may cause intolerable risk to the health of a subject because the subject was found not to satisfy the inclusion criteria specified in the protocol after enrollment or the protocol has not been observed.

6. Lost to follow-up

When subject fails to make visits and cannot be contacted. The attempts that were made to contact the subject should be recorded in the source documents.

7. Discontinuation of the entire study

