13.3.3 Efficacy analysis

13.3.3.1 Primary endpoint and analysis method

[Primary endpoint]

PFS rate 6 months after enrollment

The PFS rate 6 months after enrollment, the primary endpoint, is the gross proportion of surviving subjects without documented progression up to 6 months after enrollment, counting from the day of

CONFIDENTIAL

enrollment. Subjects with no imaging data on progression at 6 months after enrollment and subjects lost to follow-up will be included in the denominator, but will not be handled as progression-free.

The criteria for determining progression are described in “13.3.3.2 Secondary Endpoints and Analytical Methods for Them”.

[Main analysis]

The following analysis will be performed in the “full analysis set”.

PFS rate at 6 months is calculated by counting of subjects each subjects with progression, not progression, or unconfirmed at 6 months. “At 6 months” in the main analysis is defined as 24 weeks (8 weeks x 3) with time window of 2 weeks before and after. Based on the observed PFS rate at 6 months from the day of enrollment, binomial test will be conducted on the null hypothesis “value will be determined invalid at PFS rate $\leq 29\%$ ”. Significant level will be 2.5% (one-sided) in main analysis. For interval estimation, accurate 90% confidence interval (two-sided) based on binomial distribution will be used.

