7.1 Analysis set

In the phase II part of the study, statistical analysis will be performed on a “full analysis set” and “safety analysis set.” The “full analysis set” will be the main efficacy analysis set, and is defined as “subjects enrolled in phase I and II who received at least one dose of protocol treatment (RD) and satisfied all of the enrollment criteria.” RD is the recommended dose that is confirmed in the phase I part. The “safety analysis set” is defined as “subjects enrolled in phase I and II who received at least one dose of either panitumumab or TAS-102.” Additionally, the set of all subjects who are enrolled in this study is defined as “all enrolled subjects.”

The statistics representative and analysis personnel should finalize a statistical analysis plan before data fixation based on confirmation of the definition of analysis sets and appropriateness of analytical handling rules of the subject data in the analysis sets, and additional handling rules for the issues that are not determined at planning before data fixation.

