7.2 Evaluation of analysis set

7.2.1 Eligibility and analysis set

A flow chart showing the breakdown of “all enrolled subjects,” “full analysis set,” and “safety analysis set,” and reasons for patients not being included in the analysis set will be tabulated and shown with a flow chart.

Reason for exclusion of safety analysis set:

- Never received panitumumab or TAS-102

Reason for exclusion of the full analysis set

- Not meeting enrollment criteria
- Never received protocol treatment (RD)

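### The primary analysis set drops treated subjects found ineligible, without requiring pre-dose evidence or an outcome-blind decision, and the primary test is never repeated in all subjects treated at the recommended dose

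*Protocol*

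**What the plan says.** The trial is a "multi-center, open-label single-arm study" (protocol 6.1). In protocol 13.3.3.1 a "binomial test will be conducted on the null hypothesis" that the 6-month PFS rate is at most 29%, using the full analysis set. Protocol 13.3.1 limits that set to "subjects enrolled in phase I and 2 who received at least one dose of protocol treatment (RD) and satisfied all of the enrollment criteria"; here RD means the recommended dose from phase I. SAP v4.0, 7.1, applies the same rule. SAP 7.2.1 gives two reasons for leaving a subject out. One is never having received protocol treatment at the RD; the other is "Not meeting enrollment criteria". It adds nothing on when, from what evidence or by whom ineligibility is established.

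Later discovery is foreseen. Protocol 8.7, item 5, contemplates stopping treatment where "the subject was found not to satisfy the inclusion criteria specified in the protocol after enrollment", and protocol 6.2.2.2 allows about 10% for ineligible or discontinued subjects. Protocol 13.1 places a data review, which covers the evaluability of subjects, before data fixation. SAP 7.4 has one theme: what happens if follow-up is cut at the start of subsequent therapy. Every efficacy analysis in SAP 7.2.4 uses the full analysis set or a subset of it.

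**The concern.** Some criteria call for judgement: a life expectancy of three months, suspected brain metastasis, effusions needing treatment, and exclusion 18, which covers "Other patients judged by the investigator or subinvestigator to be ineligible for enrollment in the study". A rapid early course may change how a subject's baseline condition is read. When evaluability is reviewed, the site and the trial team can know each subject's 6-month status, because treatment is open and there is one arm.

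Protocol 13.3.3.1 counts subjects without 6-month imaging, and those lost to follow-up, as not progression-free. That is deliberately conservative. Classing a treated failure as ineligible takes the subject out of the denominator and so sidesteps that protection. If failures are removed more readily than successes, the estimated rate is biased upward and the test can exceed its nominal level. No planned analysis would show whether the verdict depended on such removals.

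**Working it through.** **Inputs.** Threshold rate 29%, expected rate 48%, power 80%, 47 subjects needed, target 52 (protocol 6.2.2.2). The one-sided level is 5% in protocol 6.2.2.2 and 13.3.3.4 and SAP 7.2.4.5, but 2.5% in protocol 13.3.3.1 and SAP 7.2.4.1. Both are carried through.

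**Formula.** For x progression-free subjects out of n, the exact one-sided p-value is P(X ≥ x) = Σ C(n,k) · 0.29^k · 0.71^(n−k), summed over k = x to n. The critical count is the smallest x whose p-value does not exceed the level.

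**The plan's own figure.** At 5%, n=47 has critical count 20, exact size 0.0327 and power 0.814. It is the smallest n from which exact power stays at or above 80% for every larger n checked, up to 99. The allowance gives 47 × 1.10 = 51.7, rounded up to 52. The stated 47 and 52 are reproduced.

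**Removing one failure, successes held fixed.**

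| Level | All 52 | One failure excluded | Chance of exactly this count: true rate 29% / 48% |
|---|---|---|---|
| 5% | 21/52, p=0.0519, negative | 21/51, p=0.0421, positive | 2.4% / 6.1% |
| 2.5% | 22/52, p=0.0278, negative | 22/51, p=0.0219, positive | 1.4% / 7.9% |

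In the first row the exact 90% lower limit moves from 28.9% to 29.5%, across the threshold.

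One removal is not always enough. Starting from other set sizes, the same reversal takes two removals (n=47 or 50) or three (n=51 or 54).

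**Type I error if failures could always be removed from 52.** Removal lowers the count of successes needed out of the 52:

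| Failures removed | Level 5%: needed, true size | Level 2.5%: needed, true size |
|---|---|---|
| 0 | 22, 0.0278 | 23, 0.0139 |
| 1 to 3 | 21, 0.0519 | 22, 0.0278 |
| 5 | 20, 0.0907 | 21, 0.0519 |

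The last row takes the whole 10% allowance (about 5 of 52) as excluded failures. If ineligibility were unrelated to outcome and the true rate were 29%, five exclusions would all be failures with probability 0.71^5 = 0.18, and the test would not be inflated.

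**The case against.** A reader might infer that any fact emerging after treatment can make a subject ineligible. The documents do not support that. Both lists are headed as criteria at enrollment, protocol 7.0 requires them to be confirmed beforehand, and the registration system judges eligibility (7.3.1). An early death does not in itself breach a prognosis made at enrollment, and an investigator who enrolled a patient has already made the judgement in exclusion 18. Most other criteria are objective: age, RAS status, laboratory values, prior drugs.

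There are further safeguards. The analyst is independent of the sponsor (13.0). Changes to the case report form carry an audit trail (12.1). Exclusions appear in a flow chart and a subject-level list (SAP 7.2.1, 7.2.7.2). The rule was not chosen late: it is already in SAP v1.0 of June 2016, before the planned end of enrollment in March 2017. Protocol 8.7 governs stopping treatment, not analysis sets.

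All of this stands, and it makes silent removal hard. It does not settle what evidence may be used when a subject is judged ineligible after dosing. Independence from the sponsor is not blinding to outcome, and a list shows exclusions without testing whether they changed the conclusion.

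A reader might also take 9.1% as the trial's real error rate. That is not supported either. The 10% allowance covers discontinued subjects too, discontinuation is not a reason for exclusion, and outcome-driven exclusion is a possibility, not something the documents show.

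**Conclusion.** The gap is real and modest. There is no evidence-date condition, no outcome-blind condition and no efficacy analysis in all RD-treated subjects. With 52 subjects a single exclusion can reverse the verdict at either stated level, but only at one borderline count. The capacity to drop one failure lifts type I error to about 5.2% against 5%, or 2.8% against 2.5%. The figures of 9.1% and 5.2% are upper bounds that assume five exclusions, all failures. The actual effect cannot be estimated, because the documents give no expected number of treated but ineligible subjects. The case for change is that the protection costs almost nothing and covers the primary conclusion.

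**What to change.** 1. In SAP 7.4, add the same exact binomial test and 90% interval in all subjects who received at least one RD dose, at the level adopted once the 2.5%/5% conflict is resolved, and report whether the verdict agrees with the main analysis. The existing safety analysis set is not a substitute: if phase I is repeated at a reduced dose it can also hold the six subjects treated at the first dose (6 + 52 = 58, the planned maximum). With all 52 kept, success needs 22 at 5% (power 0.831) or 23 at 2.5% (power 0.752).

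2. In protocol 13.3.1 and SAP 7.1 and 7.2.1, state that an RD-treated subject is excluded only for violating a listed criterion, shown by records dated before the first dose and decided from a listing without response, progression or survival data. State also that exclusion 18 and the life-expectancy criterion are not grounds for exclusion from the analysis once treatment has started.

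The cost is some wording, one eligibility listing and one repeated test, with no new data or visits. The all-treated estimate may differ slightly from the primary one.
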